### **B 3** Calculation of SGRQ scores

Each questionnaire response has a unique empirically derived 'weight'. The lowest possible weight is zero and the highest is 100.

Each component of the questionnaire is scored separately in three steps:

- 1 The weights for all items with positive responses are summed.
- 2 The weights for missed items are deducted from the maximum possible weight for each component. The weights for all missed items are deducted from the maximum possible weight for the Total score.
- 3 The score is calculated by dividing the summed weights by the adjusted maximum possible weight for that component and expressing the result as a percentage:

Score =  $100 \times \frac{\text{Summed weights from positive items in that component}}{\text{Sum of weights for all items in that component}}$ 

The Total score is calculated in similar way:

Score = 
$$100 \times \frac{\text{Summed weights from positive items in the questionnaire}}{\text{Sum of weights for all items in the questionnaire}}$$

The Symptoms component is calculated from the summed weights for the positive responses to questions 1-8.

The Activity component is calculated from the summed weights for the positive responses to questions 11 and 15.

The Impacts component is calculated from the summed weights for the positive responses to questions 9-10, 12-14 and 16-17.

The questionnaire requests a single response to questions 1-17. If multiple responses are given to one of these questions then averaging the weights for the positive responses for that question will be done.

The Total score is calculated by summing all positive responses in the questionnaire and expressing the result as a percentage of the total weight for the questionnaire.

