#### Handling of missing items

The Symptoms component will tolerate a maximum of 2 missed items. The Activity component will tolerate a maximum of 4 missed items. The Impacts component will tolerate a maximum of 6 missed items. Domain score will be set to missing if there are more than tolerated number of items missing.

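### SAP Appendix B 3 gives two conflicting SGRQ denominators, which produce different scores whenever an item is missed

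*SAP*

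**What the plan says.** SAP Section 3.4.4 refers to the developer's manual for the details of the algorithm and says that Appendix B 3 sets out the principle of calculation in accordance with it. Within B 3:

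- **Step 2, components:** "The weights for missed items are deducted from the maximum possible weight for each component".
- **Step 2, Total:** "The weights for all missed items are deducted from the maximum possible weight for the Total score".
- **Step 3, text:** the score comes from "dividing the summed weights by the adjusted maximum possible weight for that component", and this text leads straight into the component formula.
- **Component formula, denominator:** "Sum of weights for all items in that component".
- **Total formula, denominator:** "Sum of weights for all items in the questionnaire", introduced as being calculated in a similar way.
- **Closing sentence on the Total:** "expressing the result as a percentage of the total weight for the questionnaire".

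The missing-items rule at the end of B 3 allows partly completed questionnaires to be scored. "The Symptoms component will tolerate a maximum of 2 missed items"; "The Activity component will tolerate a maximum of 4 missed items"; the limit for Impacts is 6. A domain score becomes missing only beyond these limits.

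Change in SGRQ total score to Week 12, and the proportion of participants whose score falls by at least 4 points, are both secondary endpoints (SAP Table 2).

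**The concern.** The two denominators agree only when every item is answered, and the tolerance rule means that incomplete questionnaires will be scored. For the Total, one statement adjusts for missed items (step 2), while two do not (the formula and the closing sentence). Two competent programmers working from B 3 could therefore deliver different Totals from the same data.

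Under the printed formulas a missed item adds nothing to the numerator but stays in the denominator, so it is scored as if the participant had reported no problem. On a scale where 0 is best, this lowers the score at that visit. The effect on the endpoints depends on whether baseline or Week 12 has more missed weight. The responder endpoint is the more exposed because it has a fixed cut at a change of −4. SAP Section 3.4.4 counts a missing or non-evaluable score as non-response, yet a partly completed Week 12 form could become a response through its blanks alone.

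**Working it through.** **Inputs.** The highest response weight of each item in the B 3 weight table; the 2/4/6 tolerances; the responder rule (change of −4 or lower). The documents give no rate of missed items.

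**Check of the weight table.** The SAP prints no maximum weights, but it gives the number of items as 50.

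| Component | Items | Sum of maximum weights |
|---|---|---|
| Symptoms (questions 1–8) | 8 | 662.5 |
| Activity (11, 15) | 16 | 1209.1 |
| Impacts (9–10, 12–14, 16–17) | 26 | 2117.8 |
| Total | 50 | 3989.4 |

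The count of 50 is reproduced. The mean weight is 3989.4 / 50 = 79.8, or 2.0% of the Total.

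**Relation between the two rules.** Let P be the summed weights of positive answers, M the maximum weight and m the missed weight. Steps 2–3 give 100·P/(M − m). The printed formula gives 100·P/M. Hence printed score = adjusted score × (1 − m/M). This is exact. An assumption enters only when the adjusted score is taken as the true one, that is, when skipped items are taken to resemble answered ones.

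**Effect at one visit, adjusted Total of 50.**

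- One item: 50 × 53.9/3989.4 = 0.7 (lightest) to 50 × 96.7/3989.4 = 1.2 (heaviest); 1.0 on average.
- Four average items: 50 × (1 − 4/50) = 46.0, a drop of 4.0. The same drop needs about 5 items at a score of 40 and about 3.3 at 60.
- All 12 tolerated items, heaviest: 183.0 (Symptoms) + 335.8 (Activity) + 547.8 (Impacts) = 1066.6, or 26.7% of 3989.4. The drop is 13.4, so 50 becomes 36.6.
- All 12 tolerated items, lightest: 138.8 + 277.1 + 415.6 = 831.5, or 20.8%. The drop is 10.4.

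**Effect on change from baseline.** An illustrative simulation assumed no true change, each item positive with probability 0.5, Part 1 items set to worst or zero, and items skipped at random.

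| Items missed (baseline / Week 12) | Mean change, printed | Mean change, adjusted | Responders, printed | Responders, adjusted |
|---|---|---|---|---|
| 0 / 4 | −4.0 | 0.0 | 52% | 3% |
| 4 / 0 | +4.0 | 0.0 | 0% | 3% |
| 4 / 4 | 0.0 | 0.0 | 8% | 12% |

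Where there is a real change, equal missingness shrinks it. With 10% of the weight missed at both visits, 50 to 40 (−10) becomes 45 to 36 (−9).

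**Question 6.** This item asks how long the worst attack lasted. Its four response weights run from 41.9 to 89.7, with no zero option. Question 10, by contrast, has a not-applicable option weighted 0.0. A participant who reports no attacks at question 5 has no fitting answer to question 6. With the other Symptoms items at worst, P = 662.5 − 86.7 − 89.7 = 486.1. The full denominator gives 486.1/662.5 = 73.4. Deducting question 6 as missed gives 486.1/572.8 = 84.9.

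**The case against.** The strongest reply is that the SAP already contains the right rule. Step 2 deducts missed weights for the components and, in a separate sentence, for the Total. Step 3 names the adjusted denominator and runs into the formula, which can be read as shorthand for it, and the Total is said to follow in a similar way. Coding from the formulas alone would leave step 2 with no purpose. The SAP also points to the developer's manual, which cannot be consulted here. This much stands: B 3 is an internal conflict with a risk of miscoding. A reader might infer that the plan is to score skipped questions as zero, but the documents do not support that. Nor does the manual reference settle the conflict, since B 3 is presented as being in accordance with it and does not say which of its own lines prevails.

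A reader might also infer that the error produces false improvement, or favours active treatment. The documents do not support this either. The direction depends on which visit has more missed weight, and bias between arms would need skipping to differ by arm in a double-blind trial, for which there is no evidence. A skipped item whose true answer has zero weight causes no error under the printed formula. Neither document says whether the eDiary lets an item be skipped, so the problem may be rare.

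**Conclusion.** The conflict is real and should be removed, but it is a specification fault of limited reach. If the printed formulas are followed, each tolerated missed item lowers that visit's score: by about 1 point per average item at a Total of 50, and by 10.4 to 13.4 points when all 12 tolerated items are missed. More missed weight at Week 12 gives false improvement, more at baseline gives false worsening, and an equal share at both visits shrinks the change.

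These sizes assume that skipped items resemble answered ones. The 12-item figure also assumes that the Total is calculated only when all three domains are within tolerance, which the SAP does not state. How often any of this would happen cannot be estimated from the documents.

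Two secondary endpoints are exposed: change in SGRQ total score and the 4-point responder proportion. The FEV1 primary endpoint and the four key secondary hypotheses in SAP Section 4.1.1 do not involve the SGRQ and are unaffected.

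**What to change.** In SAP Appendix B 3:

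1. Make both printed denominators the sum of the maximum weights of all items minus the maximum weights of the missed items. The starting values are 662.5 (Symptoms), 1209.1 (Activity), 2117.8 (Impacts) and 3989.4 (Total).
2. End the closing sentence on the Total with: *of the adjusted maximum weight (step 2)*.
3. State how question 6 is scored when question 5 reports no attacks, so that an item which does not apply is not handled as missed by default. Without this line, the first edit alone would move the example above from 73.4 to 84.9.

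The cost is two denominators, one sentence and one added rule. No new data or design change is needed. The edits should be made before the SGRQ scores are programmed and before unblinding for the Primary Analysis.

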#### Item weights

The wording of the item may not correspond exactly with the wording in the current version of the questionnaire.

#### PART 1

Response	Response weight		
1) Over the past 4 weeks, I have coughed:			
Almost every day	80.6		
Several days a week	63.2		
A few days a month	29.3		
Only with respiratory infections	28.1		
Not at all	0.0		
2) Over the past 4 weeks, I have brought up phlegm (sp	utum):		
Almost every day	76.8		
Several days a week	60.0		
A few days a month	34.0		
Only with respiratory infections	30.2		
Not at all	0.0		
3) Over the past 4 weeks, I have had shortness of breath	):  :		
Almost every day	87.2		
Several days a week	71.4		
A few days a month	43.7		
Only with respiratory infections	35.7		
Not at all	0.0		
4) Over the past 4 weeks, I have had wheezing attacks:			
Almost every day	86.2		
Several days a week	71.0		
A few days a month	45.6		
Only with respiratory infections	36.4		
Not at all	0.0		
5) How many times during the past 4 weeks have you suffered from severe or very unpleasant respiratory attacks?			
More than three times	86.7		
3 times	73.5		
2 times	60.3		
1 time	44.2		
None of the time	0.0		
6) How long did the worst respiratory attack last?			
A week or more	89.7		
3 or more days	73.5		

Response	Response weight		
1 or 2 days	58.8		
Less than a day	41.9		
7) Over the past 4 weeks, in a typical week, how many good days (with few respiratory problems) have you had?			
None of the days	93.3		
1 or 2 days	76.6		
3 or 4 days	61.5		
Nearly every day was good	15.4		
Every day was good 0.0			
8) If you wheeze, is it worse when you get up in the morning?			
No	0.0		
Yes	62.0		

#### PART 2

Response	Response weight	
9) How would you describe your respiratory condition?		
The most important problem I have	83.2	
Causes me quite a lot of problems	82.5	
Causes me a few problems	34.6	
Causes no problem	0.0	
10) If you have ever held a job:		
My respiratory problems made me stop working altogether	88.9	
My respiratory problems interfere with my job or	77.6	
made me change my job		
My respiratory problems do not affect my job	0.0	
Not applicable	0.0	
11) These are questions about what activities usually make you	a feel short of breath these days.	
Sitting or lying still = TRUE	90.6	
Washing or dressing yourself = TRUE	82.8	
Walking around the house = TRUE	80.2	
Walking outside on level ground = TRUE	81.4	
Walking up a flight of stairs = TRUE	76.1	
Walking up hills = TRUE	75.1	
Playing sports or other physical activities = TRUE	72.1	
12) These are more questions about your cough and shortness of breath these days.		
Coughing hurts = TRUE	81.1	

Response	Response weight		
Coughing makes me tired = TRUE	79.1		
I am short of breath when I talk = TRUE	84.5		
I am short of breath when I bend over = TRUE	76.8		
My coughing or breathing disturbs my sleep = TRUE	87.9		
I get exhausted easily = TRUE	84.0		
13) Questions about other effects your chest trouble may have of	on you.		
My cough or breathing is embarrassing in public = TRUE	74.1		
My respiratory problems are a nuisance to my family, friends or neighbors = TRUE	79.1		
I get afraid or panic when I cannot catch my breath = TRUE	87.7		
I feel that I am not in control of my respiratory problems = TRUE	90.1		
I do not expect my respiratory problems to get any better = TRUE	82.3		
I have become frail or an invalid because of my respiratory problems = TRUE	89.9		
Exercise is not safe for me = TRUE	75.7		
Everything seems too much of an effort = TRUE	84.5		
14) These are questions about your respiratory treatment.			
My treatment does not help me very much = TRUE	88.2		
I get embarrassed using my medication in public = TRUE	53.9		
I have unpleasant side effects from my medication = TRUE	81.1		
My treatment interferes with my life a lot = TRUE	70.3		
15) These are questions about how your activities might be affe	cted by your respiratory problems.		
I take a long time to get washed or dressed = TRUE	74.2		
I cannot take a bath or shower, or I take a long time to do it = TRUE	81.0		
I walk slower than other people my age, or I stop to rest = TRUE	71.7		
Jobs such as household chores take a long time, or I have to stop to rest = TRUE	70.6		
If I walk up one flight of stairs, I have to go slowly or stop = TRUE	71.6		
If I hurry or walk fast, I have to stop or slow down = TRUE	72.3		
My breathing makes it difficult to do things such as walk up hills, carry things up stairs, light gardening such as weeding, dance, bowl or play golf = TRUE	74.5		

Response	Response weight		
My breathing makes it difficult to do things such as carry heavy loads, dig in the garden or shovel snow, jog or walk briskly (5 miles per hour), play tennis or swim = TRUE	71.4		
My breathing makes it difficult to do things such as very heavy manual work, ride a bike, run, swim fast, or play competitive sports = TRUE	63.5		
16) We would like to know how your respiratory problems usua	ally affect your daily life.		
I cannot play sports or do other physical activities = TRUE	64.8		
I cannot go out for entertainment or recreation = TRUE	79.8		
I cannot go out of the house to do the shopping = TRUE	81.0		
I cannot do household chores = TRUE	79.1		
I cannot move far from my bed or chair = TRUE	94.0		
17) Now please select the response (one only) that you think best describes how your respiratory problems affect you:			
It does not stop me from doing anything I would like to do	0.0		
It stops me from doing one or two things I would like to do	42.0		
It stops me from doing most of the things I would like to do	84.2		
It stops me from doing everything I would like to do	96.7		

#### Handling of missing items

The Symptoms component will tolerate a maximum of 2 missed items. The Activity component will tolerate a maximum of 4 missed items. The Impacts component will tolerate a maximum of 6 missed items. Domain score will be set to missing if there are more than tolerated number of items missing.

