## 3.4.4 St George's Respiratory Questionnaire

The SGRQ is a 50-item PRO instrument developed to measure the health status of patients with airway obstruction diseases (Jones et al 1991). The SGRQ yields a total score and three domain scores (symptoms, activity, and impacts). The total score indicates the impact of disease on overall health status. This total score is expressed as a percentage of overall impairment, in which 100 represents the worst possible health status and 0 indicates the best possible health status. Likewise, the domain scores range from 0 to 100, with higher scores indicative of greater impairment. Specific details on the scoring algorithms are provided by the developer in a user manual (Jones and Forde 2009). The principle of calculation of total score and domain scores in accordance with the abovementioned user manual are provided in Appendix B 3.

The SGRQ will be completed using the eDiary in accordance with the SoA (CSP Section 1.3), and a 4-week recall version will be used.

The key outcome variable for the SGRQ will be the change in total SGRQ score from baseline to Week 12, but the change in total score from baseline to Week 4 and Week 28 will also be derived (see Section 3.1.3). Change in the domain score from baseline to Week 4, Week 12 and Week 28 will also be derived.

Other variables based on SGRQ to report include:

- Proportion of participants with a decrease in SGRQ score of ≥ 4 points from baseline to Week 12 (Yes=1/No=0)
  - Yes: change from baseline SGRQ score to SGRQ score at Week  $12: \le -4$
  - No: change from baseline SGRQ score to SGRQ score at Week 12: > -4
- Proportion of participants with a decrease in SGRQ score of ≥ 4 points from baseline to Week 28 (Yes=1/No=0)
  - Yes: change from baseline SGRQ score to SGRQ score at Week  $28: \le -4$
  - No: change from baseline SGRQ score to SGRQ score at Week 28: > -4

Participants with missing or non-evaluable SGRQ score will be considered as not achieving SGRQ response.

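### SAP Appendix B 3 limits missed items for each SGRQ domain but not for the Total, so a Total is still produced when a domain is unusable

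*SAP*

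**What the plan says.** **Domain rule.** SAP Appendix B 3, Handling of missing items, gives one limit per domain. For Impacts, "The Impacts component will tolerate a maximum of 6 missed items"; the corresponding limits are 2 for Symptoms and 4 for Activity. Exceeding a limit has a single stated consequence, and it concerns the domain alone: "Domain score will be set to missing if there are more than tolerated number of items missing". The Total is not mentioned there.

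**Total rule.** Appendix B 3 builds the Total from items, not from domain scores: "The Total score is calculated by summing all positive responses in the questionnaire". For missed items, step 2 says "The weights for all missed items are deducted from the maximum possible weight for the Total score". No upper limit is given. Step 3 divides by the adjusted maximum, but the displayed Total formula has as its denominator "Sum of weights for all items in the questionnaire", with no adjustment.

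**Use of the score.** For Week 12, SAP 3.4.4 states: "The key outcome variable for the SGRQ will be the change in total SGRQ score from baseline". The same section derives the responder endpoint (a decrease of at least 4 points) and counts a missing or non-evaluable score as non-response, without defining non-evaluable. It refers to the developer's manual for scoring details and presents Appendix B 3 as the calculation principle in accordance with that manual.

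**The concern.** The protection sits on the domain scores, while the named endpoint is the Total. A questionnaire too incomplete to give an Impacts score still gives a Total, rescaled over whatever was answered. In the limit, a participant who completes Part 1 only receives a Total equal to the Symptoms score. Because non-evaluable is undefined, such a Total would pass as valid.

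Elsewhere the SAP closes this gap. One missing item blocks both the domain and total scores of the E-RS:COPD (SAP 3.4.1) and the CAT total (SAP 3.4.7). Only the SGRQ rule stops at the domain, which suggests an oversight.

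If domains differ in level, losing one shifts the Total systematically. When one visit is complete and the other is not, the shift passes straight into the change score and can create or remove a responder.

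**Working it through.** **1. Check that the weight table is read correctly.** Taking the highest weight for each single-response question, the Appendix B 3 table gives 8 Symptoms items (questions 1-8), 16 Activity items (11 and 15) and 26 Impacts items (9-10, 12-14, 16-17). The sum is 50, as stated in SAP 3.4.4 and Protocol 8.1.8.5 (8 in Part 1, 42 in Part 2).

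**2. Maximum weights.**

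| Domain | Maximum weight | Share of Total |
|---|---|---|
| Symptoms | 662.5 | 16.6% |
| Activity | 558.3 + 650.8 = 1209.1 | 30.3% |
| Impacts | 2117.8 | 53.1% |
| All | 3989.4 | 100% |

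**3. Formula with a domain wholly unanswered (steps 2 and 3).** Total = 100 x remaining positive weights / (3989.4 - weight of the absent domain). Equivalently, error = domain share x (score on the rest - score on the absent domain).

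The gap between the absent domain and the rest that produces a 4-point error is 4/0.531 = 7.5 points for Impacts, 4/0.303 = 13.2 for Activity and 4/0.166 = 24.1 for Symptoms.

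**4. Illustration.** The documents give no domain scores, so these are assumptions. For Symptoms/Activity/Impacts = 65/70/40 the positive weights are 430.6 + 846.4 + 847.1 = 2124.1, so the full Total is 2124.1/3989.4 = 53.2. Without Impacts it is 1277.0/1871.6 = 68.2. Without Activity it is 1277.7/2780.3 = 46.0. Without Symptoms it is 1693.5/3326.9 = 50.9.

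| Assumed profile | Full Total | Impacts absent | Activity absent | Symptoms absent |
|---|---|---|---|---|
| 65/70/40 | 53.2 | 68.2 (+15.0) | 46.0 (-7.3) | 50.9 (-2.3) |
| 60/75/35 | 51.3 | 69.7 (+18.4) | 41.0 (-10.3) | 49.5 (-1.7) |
| 70/80/45 | 59.8 | 76.5 (+16.7) | 51.0 (-8.8) | 57.7 (-2.0) |
| 50/50/50 | 50.0 | 50.0 (0) | 50.0 (0) | 50.0 (0) |

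**5. Just over the limit.** A domain is blanked from 3 of 8, 5 of 16 or 7 of 26 missed items, and its answered items still count in the Total. If the missed weight m is proportional and the missed items are typical of their domain, error = m/(3989.4 - m) x (full Total - domain score). For Impacts, m = 7/26 x 2117.8 = 570.2; in the 60/75/35 profile the error is 570.2/3419.2 x (51.3 - 35) = +2.7. Over the three uneven profiles:
- Impacts: +2.2 to +2.7
- Activity: -1.8 to -2.5
- Symptoms: -0.6 to -0.8

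Larger values need an extreme pattern. If the highest-weight items are missed, would all have been answered the same way, and the true Total is 50, the error reaches ±3.6 (3 Symptoms items), ±5.8 (5 Activity items) or ±9.5 (7 Impacts items).

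**6. Effect of the conflicting denominator.** If the displayed formula were programmed literally, the 65/70/40 profile without Impacts would give 1277.0/3989.4 = 32.0, an error of -21.2 instead of +15.0. A flat profile would then also be wrong: 50/50/50 without Impacts gives 935.8/3989.4 = 23.5. The two statements therefore disagree even on the direction of the error.

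**The case against.** **Size.** A reader might infer that the Total will commonly be wrong by several times the 4-point threshold. The documents do not support that. A multiple of that order needs Impacts to be wholly or largely unanswered and the domain levels to differ. An absent Activity domain gives about 2 to 2.5 times the threshold in these profiles, and an absent Symptoms domain stays below it. Just over the limits, typical errors are under 3 points. If the same items are missed at both visits, part of the error cancels in the change score. All of this stands.

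**Frequency.** The SGRQ is completed on a device, and clinic questionnaires come first at the visit (Protocol 8.1.8). Neither document says whether items can be skipped. Scoring text for missed items does not show that large blocks will be blank. This stands too.

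**The manual.** SAP 3.4.4 defers scoring details to the developer's manual, which may contain a rule for the Total. It would therefore be too strong to say that no rule exists anywhere. But the SAP does not reproduce one, and a programmer working from Appendix B 3 would compute the Total.

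**Consequence.** SGRQ is not among the four key secondary hypotheses tested by the Hochberg procedure (SAP 4.1.1). In a randomised, double-blind trial a few distorted scores would mainly add noise. A reader might infer bias between arms, but nothing in the documents provides a mechanism for it.

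**The remedy.** Setting the Total to missing would discard a questionnaire with 47 of 50 items answered (3 Symptoms items missed, error about 0.6 to 0.8 points above), yet keep one with 12 missed items spread 2 + 4 + 6. That is a real trade-off. It limits the gain from the fix but does not make an uncapped Total sound.

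**Conclusion.** The point holds as a minor defect in a stated scoring rule. As written, Appendix B 3 returns an apparently valid Total when a domain is unusable under its own limits, and this Total feeds a secondary endpoint and its responder version. The sizes in steps 4 and 5 rest on the SAP weights, on assumed domain profiles and on the adjusted denominator of steps 2 and 3; the zero error for a flat profile also depends on that denominator. Errors well above the responder cut arise mainly when most or all of Impacts or Activity is unanswered. The frequency is unknown and probably low. The primary FEV1 analysis, the sample size and the control of type I error are untouched.

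**What to change.** In SAP Appendix B 3, under Handling of missing items, add: if any of the three domain scores is missing under the item limits, the Total score is set to missing and is non-evaluable in the sense of SAP 3.4.4. In the same edit, change the denominators of the displayed formulas to the adjusted maximum used in steps 2 and 3. Do this before unblinding, so that no scoring choice is made with results in view.

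The cost is small but not nil. A few partial questionnaires are lost. A missing Week 12 Total is left unimputed in the MMRM (SAP 4.1.2) and counts as non-response (SAP 3.4.4). Baseline is more costly: the visible schedule collects the SGRQ before dosing only at SV3, and SAP 3.1.3 makes every change score missing when baseline is missing. Such a participant drops out of the SGRQ change analysis altogether and counts as a non-responder.
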